11.2.6 Reproductive Considerations

Ataluren is not genotoxic, did not affect fertility in male and female rats, and was not teratogenic in rats and rabbits. In addition, lack of sexual maturity in most of the subjects likely to be enrolled in this study limits reproductive risks. However, restriction on eligibility relating to willingness to avoid unprotected sexual intercourse in any subjects known to be sexually active is included as a general precaution.

11.2.7 Prior and Concomitant Therapies

11.2.7.1 Corticosteroids

Although not specifically approved by regulatory authorities for treatment of DMD, corticosteroids are commonly employed in this subject population [Matthews 2016]. Recently, a Centers for Disease Control and Prevention working group strongly urged consideration of corticosteroid therapy in all patients with DMD [Bushby 2010a]. A completed Phase 3 study of exon-skipping therapy in a subset of patients with DMD required corticosteroid use as an entry criterion [<http://clinicaltrials.gov/ct2/show/NCT01254019>]. Limiting eligibility to patients receiving a stable corticosteroid regimen of prednisone/prednisolone or deflazacort is expected to reduce the variability of slope of change in 6MWD (the primary endpoint), thereby minimizing the required sample size to demonstrate a statistically significant treatment effect and enhancing study feasibility.

11.2.7.2 Other Prior and Concomitant Therapies

Conventional supportive therapies will be permitted; however, efforts will be made to avoid use of concomitant medications that might confound interpretation of study results (eg, aminoglycosides) or pose a safety risk (immunosuppressive therapy other than corticosteroids). Ataluren has not proven to be allergenic in studies performed to date, but review of known allergies to excipients contained in the formulation is prudent. Other restrictions relating to recent use of experimental drugs or surgery allow candidates sufficient time to recover before proceeding to study drug dosing. Subjects are not permitted to enroll who have had changes in the use of ACE inhibitors or ARBs for the prophylaxis/treatment of cardiomyopathy within 1 month to start of study due to the potential to confound study results. Restrictions against enrollment of patients expected to have major surgical procedures during the course of the study or who have substantial respiratory or cardiac compromise are intended to avoid safety problems or gaps in study drug administration in patients who require intensive supportive care.

11.3 Methods to Reduce Bias

11.3.1 Randomization

Randomization is an accepted means to reduce bias and allows for the highest standard of evidence in documenting a treatment effect. The stratified, block randomization approach will be used. The system will assign the next available randomization number, within the list for the stratum, to the patient. Such a method allows treatment arms to be balanced with respect to the predefined stratification factors as well as for the number of subjects in each arm. The process will be established and performed centrally by an experienced CRO through an IRT system to maximize the integrity and security of the randomization and ensure appropriate access and convenience-of-use by the investigational sites.

11.3.2 Stratification

The 3 stratification factors (type of concomitant corticosteroid use at baseline [deflazacort versus prednisone/prednisolone], baseline 6MWD [<300 meters versus ≥ 300 to <350 meters versus ≥ 350 to <400 meters versus ≥ 400 meters], and baseline time to stand from supine [<5 seconds versus ≥ 5 seconds]) are included to balance allocation of patients into treatment groups by these important parameters.

Although not specifically approved by regulatory authorities for the treatment of DMD, the DMD Care Considerations Working Group strongly urges consideration of corticosteroid therapy in all patients who have DMD [Bushby 2010a]. Types of corticosteroids used in DMD included deflazacort, prednisolone, and prednisone. As prednisone is metabolized to prednisolone, prednisone and prednisolone are equipotent [Matthews 2016]. There is mixed evidence with respect to the comparative efficacy of deflazacort versus prednisone/prednisolone as treatments for DMD. Some reports have indicated that deflazacort and prednisone/prednisolone may be equivalent in improving motor function [Gloss 2016], while longer-term natural history data have associated use of deflazacort with later loss of ambulation [Bello 2015]. On the basis of the latter finding, stratification by deflazacort versus prednisone/prednisolone in DMD clinical trials has been recommended [Bello 2015].

DMD natural history studies have documented that baseline 6MWD is a significant predictor of change in 6MWD [Mazzone 2011, Goemans 2013, Mazzone 2013, McDonald 2013a, McDonald 2013b, Pane 2014a]. Therefore, it is important to ensure that the treatment arms are well balanced by baseline 6MWD. In the previous Phase 3 trial of ataluren for nmDMD, subgroup analyses showed a large treatment difference in patients with baseline 6MWD ≥ 300 meters to <400 meters. Within the ≥ 300 meters to <400 meters stratum, further stratification by <350 vs ≥ 350 meters may be important to achieve the desired balance between treatment arms. In patients with less advanced disease severity (>400 meters at baseline), 6MWD is likely to remain stable over 1 year and therefore a treatment effect of disease stabilization/slowing can be obscured. In patients with more advanced disease severity (<300 meters at baseline), there is a high risk of loss of ambulation and loss of ability to perform functional outcome measures.

Baseline time to stand from supine also significantly predicts for change in 6MWD, independently of baseline 6MWD [Goemans 2016, Mazzone 2016], with poor performance on the time to stand from supine assessment increasing the risk of markedly negative changes in 6MWD and loss of ambulation. These results have identified time to stand from supine as an important additional prognostic factor of changes in 6MWD and more generally of disease progression [Mazzone 2016]. A threshold value of approximately 5 seconds appears to differentiate between patients who are likely to show stability or improvement versus those who are likely to decline [Goemans 2016]. These observations from natural history studies have been corroborated by analyses of data from our own previous placebo-controlled trials of ataluren.

11.3.3 Blinding

Double-blind administration of study treatments is utilized to provide additional and substantial protection against motivational bias on the part of subjects, caregivers, clinic staff, and other study personnel, with respect to assessment of efficacy and safety parameters.

Several steps have been taken in the proposed protocol design to minimize the prospect of systematic unblinding. Placebo is available that is an excellent match for both unmixed and mixed ataluren in terms of appearance, texture, taste, and odor. Brothers participating in the study will receive the same treatment group designation to minimize potential compromise of study drug blinding and to reduce the chance of dosing errors within families.

Packaging and labeling is identical for both the active drug and placebo. Blinding will be done centrally rather than at sites. Access to randomization information during the course of the study will be restricted to the IRT system CRO. The focus of the interim safety reviews will be on blinded data without segregation by treatment group. The final unblinded analysis of the randomized phase of the study will only be performed when the data set is complete, and a snapshot has been frozen and archived.

Unblinding in individual subjects who experience AEs is rarely required to provide effective intervention and support. Thus, disincentives for unblinding for AEs are included in the study. Investigational personnel will not have access to information at the site that would permit unblinding, and the individual subject randomization codes will only be obtainable through an auditable process involving the IRT system. Clinic staff will be made aware that such unblinding will preclude a subject from continuing with study drug administration. Unblinding will also require discussion between the investigator and the PTC Therapeutics medical monitor; this provision is not intended to prevent an investigator from proceeding with unblinding, but to ensure that appropriate consultation is obtained, that the investigator is aware of the consequences of the unblinding for the subject's continued participation in the study, and that appropriate permission is granted to the IRT system to release the treatment assignment only for that subject.

11.4 Treatment and Safety Monitoring Plan

11.4.1 Reference Therapy

Selection of placebo as the reference arm in the proposed study is clearly appropriate given that no other approved standard therapy for nmDMD exists. Use of placebo provides an opportunity to obtain additional information regarding the full treatment effect size for ataluren.

11.4.2 Schedule and Dose Selection

Dosing based on body weight will continue to be employed. Such dosing is common in pediatrics and reduces variability in exposure by accommodating differences in subject size across the span of ages of the boys who will participate in the clinical study program.

The schedule of drug administration is derived directly from Phase 1 pharmacokinetics modeling and from Phase 2 exposure information. The intent of administering 2 smaller doses at 6-hour intervals during the day and a larger dose at a 12hour interval overnight (eg-, at 7:00 AM, 1:00 PM, and 7:00 PM) is to optimally sustain target plasma concentrations while minimizing total exposures. This schedule is likely to fit well with daily patterns of living for subjects, thus enhancing compliance. As confirmation of that premise, compliance with ataluren dosing in previous trials has been excellent.

The dose of 40 mg/kg/day is the conditionally approved dose of ataluren for DMD in Europe.

11.4.3 Duration of Therapy

Duration of therapy in this confirmatory study is consistent with the EMA and FDA guidelines for DMD clinical trial, which indicate that a duration of therapy >1 year may be necessary to demonstrate a treatment effect. Use of a placebo control beyond 72 weeks would likely be discouraging to subjects and could compromise subject participation and retention. After the double-blind treatment period ends, subjects will receive an additional 72 weeks of open-label treatment to evaluate long-term effects of ataluren on patients with this progressive disorder.

11.4.4 Safety Monitoring

In defining therapeutic activity in a particular clinical setting, it is imperative that the drug's safety profile be fully characterized. As is conventional in all clinical studies, proper description of each AE or laboratory abnormality requires an understanding of the type, incidence, timing, severity, and relatedness to study drug. For consistency of interpretation, AEs will be coded using the standard MedDRA, and the severity of these events will be graded using the well - defined CTCAE. Standard definitions for seriousness will be applied. Particular attention will be paid to any AEs causing discontinuation of ataluren and to SAEs requiring rapid regulatory reporting.

11.4.5 Concomitant Therapies

As substantial modification of corticosteroid dosing due to manifestation of undesirable side effects such as osteoporosis during the study may confound study results, investigators and subjects are encouraged to maintain corticosteroid dosing as uniformly as possible. Specific recommendations for maintaining, modifying, or discontinuing corticosteroids are provided with the protocol (see [Appendix 1](#)).

Cases of decreased renal function have been observed in patients with nmCF receiving ataluren and IV aminoglycosides together with other antibiotics for cystic fibrosis exacerbations (Section [5.4.2](#)). As a precaution, guidance has been provided to the investigator with respect to actions to be taken in the event that abnormalities are noted in renal laboratory parameters.

The investigator is encouraged to consult the PTC medical monitor with questions relating to specific drugs and their potential for interactions with ataluren.

11.5 Open-Label Treatment Period

The inclusion of a 72-week open-label treatment period following 72 weeks of double-blind treatment will allow for collection of long-term efficacy data and add to the long-term safety database.

The open-label treatment period is important for subject recruitment, retention, and compliance in this double-blind study. The assurance that all subjects can eventually receive open-label ataluren if they participate in the double-blind study will stimulate subject recruitment. The knowledge that subjects must be reasonably compliant with study procedures and persist with therapy throughout the double-blind study unless medical contraindications supervene provides strong incentives for subject reliability and retention. The understanding by parents that actions to break the blind (eg, having study medication chemically analyzed) will result in forfeiture of participation in the open-label treatment period will help to preserve the integrity of the blinding.

12 PROTOCOL VERSION HISTORY

Version 1: 23 February 2017

Version 2: 04 October 2017

Version 3: 01 August 2019

Version 4: 21 July 2020

12.1 Version 4.0: 21 July 2020

Item No.	Protocol Section	Version 4/Update	Reason/Rationale
1	Protocol Identifiers and Study Personnel	Revised list of study personnel and protocol number and date	Clarification
2	3.2	Revised phrasing of assessment timepoints	Clarification
3	4.1	Revised text to indicate enrollment targets are approximate	Clarification
4	6.1	Updated Schedule of Events to reflect that subjects transitioning to another ataluren study do not require a post-treatment follow-up visit	Clarification
5	6.2.1.5	Added language indicating that subjects who continue to receive post-study access to ataluren are not required to have a follow-up visit.	Clarification
6	6.2.10	Clarified that the Central Laboratory Manual provides detail on the timing of collection of pharmacokinetic samples	Clarification
7	7.6	Added that PTC Pharmacovigilance is also to be notified of pregnancy outcomes and that this notification is to occur within 24 hours.	Update
8	9.1	Added the word "approximately" for consistency with Section 4.1	Clarification
9	12	Updated protocol version history to reflect version 4	Update

12.2 Version 3.0: 01 August 2019

The overall reason for Version 3: The overall reasons for Version 3 were to address regulatory feedback and to provide updates.

Item No.	Protocol Section	Version 3/Update	Reason/Rationale
1	Protocol	Document date/version were updated	Update
2	Protocol Identifiers and Study Personnel	Study personnel updated	Update
3	2.1.2	Added secondary objectives: 
 Evaluate the correlation between plasma concentration of ataluren and functional outcomes to evaluate plasma pharmacokinetic (PK) profile of ataluren 	Update
4	2.2.2.1	Added: 
 Plasma PK at pre-morning dose and 2 hours post-morning dose at Week 144 	Update
5	3.2, #3, #7	3. Added: "When Version 3 is implemented or approximately 270 subjects have enrolled in the study, only subjects aged ≥ 7 to ≤ 16 who meet the mITT criteria will be eligible to enroll." 7. Added: "When Version 3 is implemented or approximately 270 subjects have enrolled in the study, only subjects who meet the mITT, 6MWD ≥ 300 meters at screening, Baseline Day 1, and Baseline Day 2 and time to stand from supine ≥ 5 seconds at Baseline Day 1 and Baseline Day 2, will be eligible to enroll."	Update
6	4.1	Number enrolled/sample size increased from ~250 to a maximum of 340 subjects; the maximum sample size of 340 subjects will include up to 162 subjects who meet the mITT criteria; deleted phrase that subjects who do not meet the mITT will be included in the ITT.	Update
7	6.1, Table 4	Added PK samples on Day 144	Update
8	6.2.7	Added thrombospondin 1 (THBS1) as a marker	Update
9	6.2.10	Added PK analysis method and sampling details	Update
10	6.3	Increased the amount of blood drawn	Update
11	7.9, Table 7	Table of AE reporting revised	Update
12	7.10	SAE reporting contact information updated	Update
13	9.1	Increased sample size	Update
14	9.4.8	Added PK statistical analysis methods	Update
15	9.5	Revised timing of analyses	Update
16	12	Added Protocol Version History	Update

APPENDIX 1 MANAGEMENT OF CORTICOSTEROIDS

A. Initiating Alternate Corticosteroids During the Study

If a subject does require initiation of an alternate corticosteroid therapy (ie. switching from prednisone to deflazacort or vice-versa) during the study, total doses should not exceed 0.75 mg/kg for prednisone and 0.9 mg/kg for deflazacort. General recommendations for corticosteroid dosing are provided in Table A below.

Table A. Guidance for Initiating Alternate Corticosteroid Treatment

Weight Range	Prednisone Dose (0.75 mg/kg)	Deflazacort Dose (0.9 mg/kg)
15-19 kg	12 mg	15 mg
20-25 kg	17 mg	21 mg
26-32 kg	22 mg	27 mg
33-39 kg	27 mg	33 mg
40 kg+	30 mg	36 mg

Subjects who require alternate corticosteroid initiation may remain on blinded study drug therapy. Changing the type of corticosteroid or the corticosteroid schedule during the study is strongly discouraged.

B. Maintaining Corticosteroid Dosage During the Study

Adjustments in corticosteroid dosage for increases in body weight are permitted but are not mandatory. If it is the practice of the investigator to adjust subjects' corticosteroid doses for changes in body weight, total doses should not exceed 0.75 mg/kg for prednisone and 0.9 mg/kg for deflazacort (see Table A above).

In addition, consistent with the standards proposed for the planned international corticosteroid optimization study [Bushby 2007], increases in total dose for any reasons should not exceed 5 mg for prednisone or 6 mg for deflazacort. For example, if a subject is receiving 22 mg QD of prednisone and it is elected to increase the dose, the total prednisone dose should not be increased beyond 27 mg QD. In addition, for subjects ≥ 40 kg, total doses should be capped at 30 mg of prednisone or 36 mg of deflazacort unless the subject was already receiving a higher dose of corticosteroids than these limits at study entry [Bushby 2007].

Subjects who require corticosteroid increases may remain on blinded study drug therapy.

C. Modifying Corticosteroid Dosage During the Study

Discontinuation of corticosteroid therapy during the study should be avoided unless clinically necessary. In the case of the development of predictable corticosteroid-related side effects, appropriate supportive care should be provided and corticosteroid dosage can be maintained (ie, not increased for the normal increase in body weight). If unacceptable corticosteroid side effects persist, the dosage can be reduced in decrements of ≤ 5 mg total dose for prednisone (≤ 6 mg total dose for deflazacort). Finally, corticosteroid administration can be stopped altogether. Specific recommendations for precautionary interventions for specific corticosteroid-related AEs are given below.

Acne

In the event of bothersome acne that may be attributable to corticosteroids, the following interventions are recommended:

- Corticosteroids should not be increased to adjust for increases in body weight and the subject should be provided with consultation from a dermatologist for institution of appropriate conventional therapy for acne.
- If the acne is so severe it cannot be managed with appropriate anti-acne measures, dosage reductions of ≤ 5 mg total dose for prednisone (≤ 6 mg total dose for deflazacort) at ~6-week intervals can be considered.
- Every attempt should be made to avoid stopping corticosteroids solely for acne; if the subject/family demands that corticosteroids be stopped, see Section D below for procedures for withdrawal of corticosteroids.

Behavior Changes

Where behavior changes are disruptive to family/school life, the following interventions are recommended:

- The subject and the family should be provided with behavioral support from a child psychologist.
- If the subject is already receiving behavioral advice under the guidance of a child psychologist, the corticosteroid dosage should not be increased to adjust for increases in body weight. Consideration can be given to administering the corticosteroid dose at night instead of in the morning.
- If there is no improvement despite behavioral advice under the guidance of a child psychologist, dosage reductions of ≤ 5 mg total dose for prednisone (≤ 6 mg total dose for deflazacort) at ~6-week intervals can be considered.
- If the severe behavioral problems continue to cause unacceptable disruption to school/ family life, corticosteroids may be stopped. See Section D below for procedures for withdrawal of corticosteroids.

Bone Fractures Due to Osteoporosis

Subjects who experience limb fractures should have fixation as directed by an orthopedic surgeon. Subjects who develop vertebral fractures can be treated with bisphosphonates (eg, pamidronate, 0.5 to 1 mg/kg/day IV for 3 days every 4 months). Subjects should not have a corticosteroid dosage adjustment due to the occurrence of fractures.

Cataracts

The development of cataracts should prompt referral to an ophthalmologist for evaluation. Subjects should not have a corticosteroid dosage adjustment due to the occurrence of cataracts.

Cushingoid Appearance

If the subject develops a Cushingoid appearance, that is unacceptable to the subject/family, the following actions are recommended:

- Corticosteroid dosage should not be increased to adjust for increases in body weight
- Reassurance and support should be provided. Counseling from a child psychologist should be considered.
- If the Cushingoid appearance remains unacceptable to child/family, dosage reductions of ≤ 5 mg total dose for prednisone (≤ 6 mg total dose for deflazacort) at ~6-week intervals can be considered.
- Every attempt should be made to avoid stopping corticosteroids solely for Cushingoid appearance; if the subject/family demands that corticosteroids be stopped, see Section D below for procedures for withdrawal of corticosteroids.

Gastrointestinal Irritation

In the event of the development of symptoms consistent with esophagitis, gastritis, or duodenitis, the following interventions are recommended:

- Treatment with supportive care (H2 antagonists, proton pump inhibitors, antacids) should be initiated and corticosteroid dosage should not be increased to adjust for increases in body weight.
- If symptoms persist for ≤ 6 weeks despite supportive care (H2 antagonists, proton pump inhibitors, antacids), a gastroenterology consultation should be obtained
- If symptoms persist despite continued supportive care (H2 antagonists, proton pump inhibitors, antacids) and gastroenterology evaluation, dosage reductions of ≤ 5 mg total dose for prednisone (≤ 6 mg total dose for deflazacort) at ~6-week intervals can be considered.
- If the gastroenterologist recommends discontinuation of corticosteroids for frank gastrointestinal ulceration, bleeding, etc, corticosteroids may be stopped. See Section D below for procedures for withdrawal of corticosteroids.

Height Gain Inhibition

In the event of an inhibition of body height increases that is unacceptable to the subject/family, the following interventions are recommended:

- Corticosteroid dosage should not be increased to adjust for increases in body weight
- Reassurance and support should be provided. Counseling from a child psychologist should be considered.
- If the failure to gain height remains unacceptable to child/family, dosage reductions of ≤ 5 mg total dose for prednisone (≤ 6 mg total dose for deflazacort) at ~6-week intervals can be considered.

- Every attempt should be made to avoid stopping corticosteroids solely for failure to gain height; if the subject/family demands that corticosteroids be stopped, see Section D below for procedures for withdrawal of corticosteroids.

Hyperglycemia or Glycosuria

Evidence of fasting hyperglycemia or $\geq 1+$ glycosuria persisting for ≥ 6 weeks should prompt the following interventions:

- Institute monitoring of glycosylated hemoglobin (hemoglobin A1c) to evaluate for evidence of chronic hyperglycemia.
- If hyperglycemia or glucosuria is only episodic and chronic hyperglycemia is not present by hemoglobin A1c, corticosteroids should not be increased to adjust for increases in body weight.
- If chronic hyperglycemia is present by hemoglobin A1c, consultation should be arranged with an endocrinologist regarding diagnostic evaluation and potential intervention for hyperglycemia
- If hyperglycemia persists and corticosteroid dose reduction is warranted, dosage reductions of ≤ 5 mg total dose for prednisone (≤ 6 mg total dose for deflazacort) at ~ 6 -week intervals can be considered.
- If the endocrinologist recommends corticosteroid discontinuation, corticosteroids may be stopped. See Section D below for procedures for withdrawal of corticosteroids.

Hypertension

Evidence of substantial hypertension (blood pressure elevation at 99th percentile + 15 mmHg for age) persisting for ≥ 6 weeks should prompt the following interventions:

- Corticosteroids should not be increased to adjust for increases in body weight. Dietary recommendations (weight reduction/sodium reduction) should be considered.
- If substantial hypertension persists, appropriate blood pressure management (eg, diuretics, beta blockers, calcium channel blockers) can be considered. If they can be avoided, angiotensin converting enzyme inhibitors or angiotensin receptor blockers should not be instituted during study drug therapy because such drugs may elevate plasma renin values and obscure monitoring for potential ataluren hypoaldosteronism.
- If hypertension persists despite continued antihypertensive therapy, dosage reductions of ≤ 5 mg total dose for prednisone (≤ 6 mg total dose for deflazacort) at ~ 6 -week intervals can be considered.
- If hypertension persists despite continued antihypertensive support and corticosteroid dosage reductions, corticosteroids may be stopped. See Section D below for procedures for withdrawal of corticosteroids.

Infections Potentially Related to Corticosteroid-Mediated Immunosuppression

Unusual opportunistic infections or unusual responses to infection potentially consistent with corticosteroid-mediated immunosuppression should prompt the following interventions:

- Corticosteroids should not be increased to adjust for increases in body weight and consultation with an infectious disease expert should be obtained.
- If infections cannot be managed with appropriate antibiotic prophylaxis or treatment, dosage reductions of ≤ 5 mg total dose for prednisone (≤ 6 mg total dose for deflazacort) at ~6-week intervals can be considered.
- If infections are clinically severe and/or persistent despite corticosteroid dosage reductions, corticosteroids may be stopped. See Section D below for procedures for withdrawal of corticosteroids.

Weight Gain

In the event of a body weight increase that is unacceptable to the subject/family, the following interventions are recommended:

- Corticosteroid dosage should not be increased to adjust for increases in body weight
- Reassurance and support should be provided. Counseling from a nutritionist should be considered.
- If the body weight increase remains unacceptable to child/family, dosage reductions of ≤ 5 mg total dose for prednisone (≤ 6 mg total dose for deflazacort) at ~6-week intervals can be considered.
- Every attempt should be made to avoid stopping corticosteroids solely due to increase in weight; if the subject/family demands that corticosteroids be stopped, see Section D below for procedures for withdrawal of corticosteroids.

D. Withdrawal of Corticosteroids

Corticosteroids should not be stopped suddenly. A tapered reduction in dosage is required to avoid risks of adrenal insufficiency. Tapering of drug dosage should follow the normal clinical practice of taking $\frac{1}{2}$ the regular dose for the first week, $\frac{1}{4}$ the regular dose for the second week, $\frac{1}{8}$ the regular dose for the third week and no study drugs thereafter. All adverse effects possibly due to corticosteroid should be monitored until resolved and subjects should be followed closely for symptoms consistent with adrenal insufficiency. Subjects who require corticosteroid discontinuation may remain on blinded study drug therapy.

E. Reinstitution of Corticosteroids

In subjects who discontinue corticosteroids after following the recommended interventions and corticosteroid dosage modification procedures, reinstitution of corticosteroids is not generally recommended unless adrenal insufficiency is detected. However, if reinstitution of corticosteroids is deemed necessary, the corticosteroid dosage should be lower than the lowest total dose that previously proved intolerable. Subjects who require corticosteroid reinstitution may remain on blinded study drug therapy.

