5.4.1 Corticosteroids

Corticosteroid therapy in DMD improves muscle strength and function in the short term [Matthews 2016]. To minimize potential confounding effects of changes in corticosteroid therapy on the interpretation of study results, the use of these medications must be standardized as much as possible during the study.

A stable and standardized corticosteroid regimen should be maintained during the 72 weeks of double-blind study drug treatment. Adjustments in corticosteroid dosage for increases in body weight are permitted (only once during the 72-week double-blind study treatment) but are not mandatory. Upward adjustments in corticosteroid dose for increases in body weight or other reasons should follow recommendations provided in [Appendix A](#).

If a subject experiences a concerning AE related to systemic corticosteroid use, interventions or potential adjustments in the corticosteroid dosage may be considered, as detailed in [Appendix A](#). It should be emphasized that reductions in corticosteroid dosage for cosmetic or other minor reasons should be avoided. Subjects who require corticosteroid interruption, dose modification, or reinstitution may remain on blinded study drug therapy.

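### For lighter boys in each weight band below 40 kg, the fixed corticosteroid dose in Appendix 1 Table A exceeds the mg/kg ceiling that the same appendix sets

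*Protocol*

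**What the plan says.** Appendix 1 Section A covers a switch from one steroid to the other during the study. It states that "total doses should not exceed 0.75 mg/kg for prednisone and 0.9 mg/kg for deflazacort", and continues: "General recommendations for corticosteroid dosing are provided in Table A below". Table A is titled as guidance and gives a single prednisone dose and a single deflazacort dose for each weight band. Its column headings carry the same two figures as the ceiling, 0.75 and 0.9 mg/kg. The first three rows read "15-19 kg 12 mg 15 mg", "20-25 kg 17 mg 21 mg" and "26-32 kg 22 mg 27 mg" (band, prednisone, deflazacort). The remaining rows give 27 and 33 mg for 33 to 39 kg, and 30 and 36 mg from 40 kg upward.

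Section B covers dose increases as a boy gains weight. It repeats the same ceiling and points back to Table A in the same sentence. It also limits any increase to 5 mg of prednisone or 6 mg of deflazacort, and from 40 kg caps the total at 30 or 36 mg unless the boy was already above that at entry.

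Protocol Section 5.4.1 explains why steroid dosing is controlled: "the use of these medications must be standardized as much as possible during the study". It sends upward dose adjustments to the corticosteroid appendix. It calls this Appendix A, and the only such appendix is Appendix 1.

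**The concern.** A mg/kg ceiling rises continuously with weight, whereas a banded table holds the dose flat across a range of weights. Both can hold everywhere only if each band's dose is set from the lightest boy in it. Table A's doses are not set that way below 40 kg. For the lighter boys in those bands, the ceiling allows one dose and the table lists a higher one. Nothing in the appendix permits rounding or a temporary excess within a band.

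The affected weights arise in ordinary use. A growing boy enters each new band at its light end, which is where the two rules diverge. The permitted increments of 5 and 6 mg equal the table's steps between the four closed bands (12, 17, 22, 27 mg; 15, 21, 27, 33 mg), and Section B's own worked example, 22 to 27 mg of prednisone, is one of those steps. A boy who reaches 33 kg on prednisone finds 27 mg in the table and 0.75 × 33 = 24.75 mg under the ceiling. Two sites could dose boys of equal weight differently, each citing the protocol, and a deviation review could not say which had departed from it.

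**Working it through.** **Inputs.** All come from Protocol Appendix 1: the ceilings (0.75 mg/kg prednisone, 0.9 mg/kg deflazacort; Sections A and B) and the band limits and doses in Table A. The appendix gives no derivation for the fixed doses, so there is no stated formula to reproduce.

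**Formulas.** mg/kg at the bottom of a band = listed dose ÷ lowest weight. Ceiling dose = ceiling × lowest weight. Excess = listed dose − ceiling dose. Crossover weight = listed dose ÷ ceiling; below it, and within the band, the listed dose is over the ceiling.

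**Prednisone (ceiling 0.75 mg/kg)**

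| Band, kg | Dose, mg | mg/kg at lowest weight | Ceiling dose, mg | Excess, mg | Over the ceiling below |
|---|---|---|---|---|---|
| 15–19 | 12 | 12/15 = 0.800 | 11.25 | 0.75 (6.7%) | 16.0 kg |
| 20–25 | 17 | 17/20 = 0.850 | 15.00 | 2.00 (13.3%) | 22.7 kg |
| 26–32 | 22 | 22/26 = 0.846 | 19.50 | 2.50 (12.8%) | 29.3 kg |
| 33–39 | 27 | 27/33 = 0.818 | 24.75 | 2.25 (9.1%) | 36.0 kg |
| 40+ | 30 | 30/40 = 0.750 | 30.00 | 0 | none |

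**Deflazacort (ceiling 0.9 mg/kg)**

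| Band, kg | Dose, mg | mg/kg at lowest weight | Ceiling dose, mg | Excess, mg | Over the ceiling below |
|---|---|---|---|---|---|
| 15–19 | 15 | 15/15 = 1.000 | 13.50 | 1.50 (11.1%) | 16.7 kg |
| 20–25 | 21 | 21/20 = 1.050 | 18.00 | 3.00 (16.7%) | 23.3 kg |
| 26–32 | 27 | 27/26 = 1.038 | 23.40 | 3.60 (15.4%) | 30.0 kg |
| 33–39 | 33 | 33/33 = 1.000 | 29.70 | 3.30 (11.1%) | 36.7 kg |
| 40+ | 36 | 36/40 = 0.900 | 36.00 | 0 | none |

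**Extent within the bands.** Of the 25 whole-kilogram weights from 15 to 39 kg, the prednisone dose is over the ceiling at 1 + 3 + 4 + 3 = 11 and the deflazacort dose at 2 + 4 + 4 + 4 = 14. At the top of every closed band the dose is under the ceiling: prednisone 0.632 to 0.692 mg/kg, deflazacort 0.789 to 0.846 mg/kg.

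**A likely origin.** Ceiling × band midpoint (17, 22.5, 29, 36 kg) gives 12.75, 16.88, 21.75 and 27.00 mg for prednisone and 15.30, 20.25, 26.10 and 32.40 mg for deflazacort. Every listed dose is within 1 mg of these. The table looks like a mid-band rendering of the same mg/kg figures, which would put the lighter boys in each closed band over the ceiling. This is an inference from the numbers; the appendix does not say so.

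**The case against.** The strongest reply is that the text already ranks the two rules. The ceiling is a limit, while the table is introduced as general recommendations and titled as guidance, so a site that gives less than the listed dose to stay under the ceiling breaks nothing binding. The matching column headings also suggest that the table is only a rounded form of the ceiling. This has some force, but it does not remove the conflict. Section B cites the table beside the ceiling as if they agreed, Section 5.4.1 makes the appendix the reference for upward adjustments, and no sentence says that the ceiling overrides the table or that rounding is allowed.

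The objection about exposure does stand. The appendix advises strongly against changing steroid type, weight adjustments are optional and allowed only once in the 72 double-blind weeks, and each excess is smaller than the appendix's own maximum step of 5 or 6 mg. The open-label SAP (Section 1) records the first database lock in April 2022, after all subjects had completed double-blind treatment. Correcting the appendix now cannot change conduct in the primary comparison.

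A reader might also infer more than the documents support:

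- That Table A is over the ceiling throughout four bands, or that no site can follow both rules. For heavier boys in each band both can be followed.
- That the ceiling is a safety limit. Appendix 1 gives it no safety rationale. Section 5.4.1 gives confounding as its reason for standardizing steroid use, and Table 1 of the protocol lists the same two figures as recommended daily doses.
- That the stratified comparison is compromised. Stratification is by steroid type at baseline, not by dose on study, and the same table applies to both blinded arms, so no differential bias is shown.

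**Conclusion.** The inconsistency is real and limited in extent. Ceiling and table disagree for the lighter boys in each of the four bands below 40 kg, for both drugs. The largest proportional excess is at 20 kg (0.85 mg/kg prednisone, 1.05 mg/kg deflazacort), and the largest in milligrams is at 26 kg (2.5 and 3.6 mg).

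This rests on two assumptions: that the ceiling and the table refer to the same daily total, as the shared mg/kg figures in the column headings and the once-daily example in Section B indicate, and that the bands are read in whole kilograms as printed. How many boys were dosed at the affected weights is unknown, because the documents report neither the weight distribution nor the frequency of switches or adjustments.

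The consequence is an ambiguous instruction on a treatment that the protocol wants held uniform, and no clear standard for judging deviations. No effect on the primary result is demonstrated.

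**What to change.** Reconcile Table A with the ceiling in Sections A and B so that text and table give the same instruction at every weight. If one is meant to prevail, or if rounding within a band is intended, the appendix should say so. Which of the two governs is for the sponsor's medical team, and this review takes no view. The change touches one table or one sentence of Appendix 1 and needs no change to the analysis. With the double-blind period complete, its remaining value is for any continuing open-label use, for the review of steroid-related protocol deviations, and for any later study that reuses this appendix.
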